8 ASSESSMENT OF IMMUNOGENICITY

8.1 Enzyme-linked Immunosorbent Antibody Assay (ELISA)

The serum IgG levels against the respective antigens will be measured, as previously described.^{15,17,18} Briefly, 96-well plates are coated with the respective COPS, Vi, or FliC antigen (5 µg/mL). After overnight incubation, plates are washed and sera are tested in serial dilutions. Specific antibodies will be detected using peroxidase-labeled anti-human IgG and 3,3,5,5-Tetramethylbenzidine (TMB) substrate. Test and control sera are run in duplicate. Titers are calculated by interpolation of absorbance values of test samples into the linear regression curve of a calibrated control (reference serum). The endpoint titers will be reported as ELISA units (EU), which represent the inverse of the serum dilution that produces an absorbance value of 0.2 above the blank. Seroconversion will be defined as a 4-fold increase in the antibody titer after immunization.

8.2 Opsonophagocytic Activity (OPA) assay

The OPA assay is to be performed as previously described^{38,39} with some modifications to the originally described Lindow et al. method.⁴⁰ Heat-inactivated serum samples will be added to bacteria and incubated for 30 min at 37°C to allow for antibody binding (opsonization). THP-1 macrophage monolayers will be incubated with opsonized bacteria in antibiotic-free medium for 30 min. (OPA) and 24 hr (survival analysis). Following incubation, extracellular bacteria will be killed (using gentamicin) and for the opsonophagocytosis assays, macrophages will be lysed and the lysate will be plated onto LB plates, for enumeration of the colony forming units (CFU). For the survival assays, plates will be incubated overnight and the surviving bacteria will be counted by lysing and plating the cell lysates onto LB plates as described above.

8.3 Serum Bactericidal Activity (SBA) assay

The SBA assay is planned to be performed as previously described.⁴¹ Bacteria, from log-phase cultures, are added to a plate for incubation with guinea pig complement and/or baby rabbit complement. Serially diluted heat-inactivated serum samples will be added to the plate. The SBA antibody titer will be defined as the reciprocal of the highest serum dilution that produces >50% killing in relation to the killing observed for the control wells containing bacteria and complement only (i.e., no serum). The titers will be determined from the mean bacterial count from triplicate wells.

8.4 Antibody Secreting Cells (ASC) assay

Plasmablasts secreting antibodies that recognize the respective COPS, Vi, FliC, or TT antigen will be measured using ELISPOT, using previously described methods.⁴² The frequency of spot-forming cells (SFC) from replicate wells will be determined and reported as ASC/10⁶ PBMC. A positive response will be defined as ≥8 ASC/10⁶ PBMC. Antibodies in lymphocyte supernatants (ALS) from these plasmablasts may also be collected and tested using the ELISA assay. From some PBMCs there may be the measurement of the mucosal homing potential of plasmablasts. PBMC will be enumerated by flow cytometry based on molecules expressed in naïve (B_n;

CD19+ IgD+ CD27-) and memory B (B_M; CD19+ IgD- CD27+) cells which direct them to home to distinct sites (e.g., integrin $\alpha 4\beta 7$, CD62L, CXCR3).

8.5 Circulating B cell memory cells (BM) and Cell-mediated Immunity (CMI) (cytokines, T cell effector and memory (including circulating T follicular/helper cells -cT_{fh}-), T cell homing

Blood will be drawn before each vaccination (Days 1, 29, and 57) and on Days 85 and 209 post-vaccination and isolated PBMC cryopreserved for studies of specific BM⁴³⁻⁴⁵ and CMI⁴⁶⁻⁵⁰ responses, including cytokine production (e.g., interferon- γ) and expression of homing molecules in effector and memory T cells which might direct them to either mucosal or systemic effector sites. Antigen specific cytokine-production and induction of effector and memory T cells, as well as cT_{fh}, will be measured in cryopreserved PBMC stimulated with the appropriate antigens (e.g., FliC, tetanus toxoid). Antigen-stimulated PBMC will be stained for conventional flow cytometry (using fluorochrome-conjugated monoclonal antibodies) or mass cytometry (using metal-conjugated monoclonal antibodies), run in the corresponding instruments, and the data analyzed using supervised and non-supervised flow cytometry analytical packages. The frequency of BM specific for COPS, Vi, FliC, and tetanus toxoid antigens will be measured by a previously described ELISPOT-based assay.

8.6 Antibodies in Oral Fluid

As opposed to IgA-rich saliva, oral crevicular fluid (the fluid found in the crevice between the tooth and the gum) is a transudate of serum that is ~1% of the IgG concentration of the blood. Using the same method of measure serum ELISA antibody, the antibodies in oral fluid will be measured against Vi polysaccharide, TT, FliC, and COPS. (reference: Tapia MD, asetti MF, Cuberos, L, et al. *Pediatr Infect Dis J* Sept 2006; 25(9): 819-825)

9 QUALITY AND MONITORING

9.1 Quality Control and Quality Assurance

All clinical trials conducted by the University of Maryland Center for Vaccine Development (CVD) are internally audited for quality assurance (QA) quality control (QC) under the CVD-Wide Quality Management Plan (QMP). The purpose of the QMP is to describe QA/QC procedures designed to ensure site and investigator compliance with applicable regulations, adherence to the IRB-approved protocol, generation of credible, quality data, protect data integrity, and safeguard the safety and well-being of study participants. The plan has the authority to enforce and correct clinical and laboratory deficiencies observed during the conduct of a trial/research study.

Quality Management (QM) activities will proceed in compliance with E6(R2) Good Clinical Practice: Integrated Addendum to ICH E6(R1), March, 2018. Consistent with the University of Maryland Center for Vaccine Development site-wide QMP, a Protocol-specific Quality Management Plan (QMP) (Appendix B of the site-wide QMP) of the will be developed for this protocol. The Protocol-specific plan applies a risk-based approach to Quality Management (QM) focused on the essential elements of clinical trial conduct, i.e., recruitment strategies, the informed consent process, eligibility, study-related procedures, clinical and safety assessments, AEs/SAEs, study product management, specimen management, and data management. The plan will also outline site delegation of QC/QA responsibilities, frequency of regulatory file reviews, the audit schedule (e.g., sample size, audit frequency, critical data that will be reviewed, communication, etc.), documentation and reporting of QA findings/queries, and the development of corrective action preventive action (CAPA) plans (as indicated).

Pharmaron will implement a site-specific QMP, similar to the CVD's QMP and following the CVD's standards.

9.2 Clinical Monitoring

Site monitoring is conducted to ensure that the rights and well-being of human subjects are protected, that the reported trial data are accurate, complete, and verifiable, and that the conduct of the trial is in compliance with the currently IRB-approved protocol/amendment(s), with GCP, and with applicable regulatory requirement(s). Monitoring refers to the methods used by sponsors of investigational studies, or Contract Research Organizations (CROs) delegated site monitoring responsibilities, to oversee the conduct of, and reporting of data from, clinical investigations. Site monitoring includes ensuring appropriate clinical investigator supervision of study site staff and third party contractors.

In order to ensure protocol compliance, monitoring visits by a sponsor-designated professional or monitor will occur at scheduled intervals. The visit frequency will be defined in a monitoring plan (refer to Section 8.1 below) and communicated before study start to the principal investigator and all other appropriate study personnel.

9.3 Site Monitoring Plan

Independent site monitoring will be conducted to assess the progress of the clinical trial and ensure that the rights, safety, and well-being of study participants are protected, study procedures, laboratory procedures, study intervention administration, and data collection processes are of high quality that comply with ICH/GCP, federal, state, and local regulatory authorities and that the study is conducted in accordance with the IRB-protocol and sponsor standard operating procedures (SOPs). Clinical monitoring of this protocol will be performed by qualified individuals selected by the sponsor in accordance with ICH/GCP (Section 5.18.2) and as detailed in the monitoring plan.

Site visits will be made at standard intervals as defined by the sponsor. Monitoring visits will be performed in accordance with ICH/GCP (Section 5.18) and will include, but are not limited to, review of regulatory files, participant study charts inclusive of DCFs and source documents contained therein, informed consent forms, study product accountability records, medical and laboratory reports, etc. Study monitors will meet with investigators to discuss visit findings, any problems and/or issues and actions to be taken, if any. The principal investigator will be responsible for review, follow-up and resolution of monitoring findings

10 STATISTICAL CONSIDERATIONS

10.1 Study Hypothesis and Sample Size Considerations

The overarching hypothesis of this phase 1 study is that the trivalent *S. Enteritidis/S. Typhimurium/S. Typhi* Vi conjugate vaccine will be well-tolerated at all three dosage levels tested and that the highest dosage level will elicit the strongest serum anti-COPS, anti-FliC and anti-Vi antibody responses in humans. The primary hypothesis of safety will be fulfilled if no participants develop a vaccine related SAE and each vaccine is well-tolerated. The secondary hypothesis of immunogenicity will be fulfilled if each vaccine elicits an immune response by ELISA.

The trial sample size is intended to minimize the number of subjects exposed to each vaccine until sufficient safety data have accumulated to proceed to larger trials. The phase 1 trial sample size was not derived to achieve a pre-specified statistical power. Instead, the sample size was selected to descriptively evaluate the safety and immunogenicity of these vaccines in a first-in-man trial. As a result, there will be sufficient power to detect only very large differences in immunological responses among groups, and confidence limits will be fairly wide.

The endpoint measures for the primary, secondary and exploratory objectives are listed in Sections 6.1, 6.2 and 6.3.

10.1.1 Sample size in Part 2 of the study

The adaptive design for the Part 2 portion of this study will involve the evaluation of single dose vs. two-dose regimens of the trivalent vaccine, in comparison to placebo. There is a theoretical possibility of immunological “interference” with the addition of antigens in multivalent glycoconjugate vaccines.⁵¹ Under such circumstances, the responses to some antigens may be reduced. There is no expectation for there to be differences in the seroconversion rates between single dose and two-dose regimens of glycoconjugate vaccines in healthy U.S. adults.⁵² On the other hand, the design of Part 2 of the study will substantiate moving forward with two-dose regimens in sub-Saharan Africa where we do expect that more than a single dose will be required in the target pediatric population^{53,54}—so the purpose is the demonstration of safety with two sequential doses and not for showing differences in immune responses.

10.2 General Statistical Principles

Descriptive Statistics. To summarize safety, the number and percentage of participants in each cohort that experiences each AE, categorized by body system and preferred term, will be tabulated with by vaccine received along with a corresponding two-sided exact 95% confidence interval (95%CI). For seroresponse rate endpoints, two-sided 95%CI for each proportion will be calculated. When determining GMT antibody titer, the log values will be used to construct the 95%CI using the t-distribution for the mean difference between three pair-wise vaccine groups. The mean difference and the corresponding CI limits will then be exponentiated to obtain the GMT ratio and corresponding CI. If the values deviate from a log normal distribution, then a non-parametric method may be used for the analysis of GMT.

Continuous Measures of Immune Response. Continuous variables of interest that are not normally distributed will be transformed if needed. To compare each vaccine dose group with the placebo group, t test or Mann-Whitney U test will be used for continuous variables as appropriate

Multiple Comparisons. No formal statistical adjustment for multiple comparisons is planned. The investigators recognize that the study involves multiple comparisons (among vaccine doses, between vaccines, etc.) of safety and immunogenicity parameters, and that statistically significant results could be obtained in some cases when there is no difference between the groups being compared. However, such instances (type I errors) should be infrequent; e.g., if we use $p < 0.05$ as the criterion for statistical significance, only 5% of all comparisons that are actually equivalent will be significant. Moreover, it is difficult to know exactly which comparisons should be included in an adjustment. (We would not want to include safety assessments, because the error of assessing a safe vaccine as unsafe is preferable to thinking that a truly unsafe vaccine is safe.) The main purpose of this trial is to provide data for making decisions about further study of this vaccine, and statistical significance per se is not the only criterion for decision-making in this process. Nevertheless, the investigators will keep the issue of multiple comparisons in mind when interpreting the data and making decisions, even though no formal adjustment is made.

Analyzable Subjects. All vaccinated subjects will be included in the reactogenicity analysis even if they have missing data points. All vaccinated subjects will be included in the immunogenicity analysis if they donated at least one pre-vaccination and one post-vaccination specimen.

COVID-19. For participants in Cohort C, COVID-19 testing (both PCR and antibody) will be performed. Because of the potential for COVID-19 infection (either acute infection or recent prior infection) to alter immune responses, there will be the intent to stratify the analysis according to positive or negative COVID-19 infection.

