1 BACKGROUND

1.1 Epidemiology and Burden of Disease

Salmonella enterica serovars Typhi and Paratyphi A and B and certain non-typhoidal *Salmonella enterica* (NTS) serovars are important causes of invasive *Salmonella* disease worldwide. “Typhoid Fever” is caused by *Salmonella enterica* serovar Typhi (S. Typhi), while “Paratyphoid Fever” is caused by *Salmonella enterica* serovar Paratyphi A (S. Paratyphi A) or *Salmonella enterica* serovar Paratyphi B (S. Paratyphi B). Both Typhoid Fever and Paratyphoid Fever manifest as persistent fevers, abdominal discomfort, headache and malaise. Without prompt and effective antibiotic treatment, these infections may lead to intestinal hemorrhage, intestinal perforation and peritonitis, myocarditis, hepatitis, neurological consequences and death. In the pre-antibiotic era the case fatality rate of typhoid fever was circa 15%.

In industrialized countries in North America, Europe and in Australia and New Zealand, various NTS serovars are common causes of gastroenteritis, as the result of sporadic food-borne transmission or associated with outbreaks. In older children and adults, these NTS infections typically result in uncomplicated diarrheal illness that does not require antibiotic treatment and invasive infections due to NTS serovars in healthy adults are rare. However, among certain sub-populations (such as infants < 3 months of age, the elderly, and immunocompromised hosts) in industrialized countries, invasive NTS (iNTS) infections such as bacteremia, septicemia, and meningitis can be observed and are associated with notable case fatality.^{2,3} The most common *Salmonella* serovars associated with invasive disease in the U.S. include: S. Typhimurium, S. Enteritidis, S. Heidelberg, S. Dublin, and S. Schwarzengrund.⁴

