2.4 Secondary Objectives and Outcome Measures

The secondary objectives and outcome measures of this study are the following:

1. Safety: To assess the frequency and severity of abnormalities in clinical safety laboratory parameters at 7 days following the first dose of vaccine.
2. Immunogenicity: To measure the proportion of subjects that achieve a four-fold increase in titer, as compared to baseline, of specific serum IgG anti-COPS (S. Enteritidis or S. Typhimurium), anti-Vi (S. Typhi) polysaccharide, and anti-FliCn (S. Enteritidis or S. Typhimurium) antibody at day 180/210, as measured by ELISA.
3. Immunogenicity: To calculate the GMT of serum IgG anti-COPS (S. Enteritidis or S. Typhimurium), anti-Vi polysaccharide, and anti-FliC (S. Enteritidis or S. Typhimurium) antibodies at days 1, 29, 57, and 180/210, as measured by ELISA.

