6.2 Visit 1 - Enrollment & Vaccination Dose #1 (Day 1)

A participant that satisfies eligibility will be given an appointment for enrollment. The following activities will be completed prior to vaccination:

- interim medical history or concomitant medications
- A targeted physical examination, if indicated based on review of interim medical history
- Measure oral temperature, blood pressure, and pulse
- Final review of all inclusion and exclusion criteria
- A blood volume of 15 mL for the collection of serum, 80 mL for the collection of peripheral blood mononuclear cells (PBMC), and 12.5 mL for safety laboratory assessment, consisting of:
 - Hematology (4 mL, lavender, EDTA tube): total WBC, ANC, Hg, platelets
 - Chemistry (8.5 mL, red, serum separator tube): creatinine, AST, ALT, TBIL, CRP
 - SARS-CoV-2 antibody test (5 mL), to be performed at University of Maryland Pathology Associates (UMPA)
- Collect nasopharyngeal swab for SARS-CoV-2 PCR test, to be performed at University of Maryland Pathology Associates (UMPA)
- For women of child-bearing potential, a urine pregnancy will be performed
- Collect oral fluid (crevicular fluid)
- Confirmation of ongoing informed consent

Enrollment and randomization may be performed after eligibility has been confirmed. Once randomization has been completed, a prospectively assigned unblinded vaccinator and unblinded checker will check the randomization treatment assignment and prepare the masked study product. The injection site will be cleaned with an alcohol swab. The assigned study product will be administered to the deltoid muscle by intramuscular route. The study product administered, the location, and time of administration will be documented on the appropriate source document.

Following receipt of dose #1 of study product, the participant will be directly observed for at least 20 minutes. The PI (or designee) may determine that a participant requires longer on-site observation or clinical assessment, as needed for significant adverse events. Prior to discharge, the participant will be provided with training on the completion of a *Memory Aid*, given a digital thermometer, and provided follow-up visit information and contact phone numbers for study staff.

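### The secondary GMT and other continuous titer comparisons name no adjustment for the Day 1 titer, although it is available for everyone analyzed; low severity, with a gain that depends on an unstated correlation

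*Combined protocol and SAP*

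**What the plan says.** Section 10.2 describes two between-group titer analyses. For GMTs, "the log values will be used to construct the 95%CI using the t-distribution for the mean difference between three pair-wise vaccine groups", with the difference then exponentiated to a GMT ratio. For other continuous immune measures, "To compare each vaccine dose group with the placebo group, t test or Mann-Whitney U test will be used for continuous variables as appropriate". Neither names a baseline covariate, and the continuous variables of interest are not listed.

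The Day 1 titer will exist. Under Analyzable Subjects in the same section, participants enter the immunogenicity analysis "if they donated at least one pre-vaccination and one post-vaccination specimen". Section 6.2 lists, among the steps before vaccination, "A blood volume of 15 mL for the collection of serum". Section 2.4 treats Day 1 as a GMT time point in its own right: "antibodies at days 1, 29, 57, and 180/210, as measured by ELISA".

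Two other passages limit the reach of the point. The primary immunogenicity outcome in Section 2.3 is a four-fold rise over the participant's own baseline. The dose-selection benchmark in Section 10.3 is a response rate of, optimally, at least 70%, and Section 8.1 defines seroconversion as a four-fold rise.

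**The concern.** Section 2 gives Cohort C five randomized arms of 6, 6, 4, 4 and 2. In arms this small, randomization often leaves the groups at different starting titers. If Day 1 titer predicts post-vaccination titer, part of that difference appears in the unadjusted GMT ratio. Some baseline variation is plausible for the non-typhoidal antigens, since Section 1.1 notes that in industrialized countries "various NTS serovars are common causes of gastroenteritis". It reports no baseline titers, however, and says nothing about Vi.

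At stake is how the between-dose and one- versus two-dose titer contrasts are read. Section 10.1 expects the highest dosage to give the strongest responses. The synopsis warns that Part 2 may not be conducted, in which case Cohort C would supply the only randomized titer evidence on those questions.

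**Working it through.** The plan gives no SD, effect size or correlation for titers, so it has no figure to reproduce. Work in units of the log-titer SD (set to 1), with a common SD across arms. Let rho be the correlation between Day 1 and post-vaccination log titer. It is **assumed** at 0, 0.3, 0.5 and 0.7.

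**1. Chance baseline gap.** The SD of the difference in baseline means is sqrt(1/n1 + 1/n2).
- 6 v 6: sqrt(1/6 + 1/6) = 0.58; chance of a gap above 0.5 SD = 39%.
- 6 v 2: sqrt(1/6 + 1/2) = 0.82; chance = 54%.
- 4 v 2: sqrt(1/4 + 1/2) = 0.87; chance = 56%.

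**2. What an unadjusted contrast carries.** This is rho × gap. For a 0.5 SD gap it is 0.15, 0.25 and 0.35 SD at rho 0.3, 0.5 and 0.7. Against the 6 v 6 half-width of 1.25 SD in step 3, that is 12%, 20% and 28% of the half-width.

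**3. Mean 95% half-width, 6 v 6 in Cohort C.** Here c is the mean of the estimated SD divided by the true SD.
- Two-group t, 10 df: 2.228 × 0.975 × 0.577 = 1.25.
- Five-arm model without baseline, 22 − 5 = 17 df: 2.110 × 0.985 × 0.577 = 1.20. The ratio to t is 1.20/1.25 = 0.96, so variance pooling alone gives 4 to 5 points.
- Five-arm model with log Day 1 titer, 16 df: approximately 2.120 × 0.985 × 0.577 × sqrt(1 + 1/15) × sqrt(1 − rho²) = 1.24 × sqrt(1 − rho²). The 1/15 term is the average cost of baseline imbalance.

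Simulated half-widths for the third model, with coverage close to 95%:

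| Assumed rho | Half-width (SD) | Ratio to two-group t | Ratio to five-arm model without baseline |
|---|---|---|---|
| 0 | 1.24 | 0.99 | 1.04 |
| 0.3 | 1.18 | 0.94 | 0.99 |
| 0.5 | 1.08 | 0.86 | 0.90 |
| 0.7 | 0.89 | 0.71 | 0.74 |

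The last column isolates baseline: a small loss at rho 0, almost nothing at 0.3, and a real gain at 0.5 and above.

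**4. Day 29 with equal-dose arms merged.** Dose 2 has not yet been given when the Day 29 specimen is drawn (Section 6.5), so the arms can be read as 12, 8 and 2. For 12 v 8 the two-group t gives 0.945 SD. The adjusted model gives 0.97, 0.93, 0.84 and 0.69 SD, which is about 3% wider at rho 0 and narrower after that.

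**5. Where adjustment can hurt.** Fitted inside Cohort A (8 v 2) at rho 0, the half-width rises from 1.76 to 1.94 SD (+10%). Inside Cohort B (10 v 2) it rises from 1.68 to 1.80 SD (+7%). At rho 0.3 both are still wider, by 5% and 2%. A two-group adjusted model for 6 v 6 breaks even only near rho 0.36, against the two-group t.

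**The case against.** The strongest reply is that unadjusted comparisons are valid under randomization within a cohort, so this is a preference about efficiency. Section 10.1 calls the evaluation descriptive and warns of wide limits, and Section 10.1.1 says Part 2 is not meant to show differences in immune response. That stands, and it is why the severity is low. Wide expected limits are still a reason to use data already in hand.

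A second objection concerns the model. It assumes one slope and one residual variance in placebo and vaccine arms. Titers of unvaccinated participants may follow Day 1 closely and those of responders less so. With 2 placebo recipients this cannot be checked. That also stands, and it bears most on the placebo contrasts.

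A reader might go further in four ways that the documents do not support:
- *That the planned intervals are simply too wide.* This depends on a correlation given nowhere, and part of the apparent gain is variance pooling.
- *That adjusting costs at most about 3%.* This fails for placebo contrasts within Cohort A or B.
- *That the primary endpoint or dose selection is compromised.* Both rest on rises from the participant's own baseline.
- *That the plan excludes any analysis of change.* Section 10.2 does not list its continuous variables, so fold-rise is neither planned nor ruled out.

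**Conclusion.** The gap is real but limited. The secondary GMT ratios and other continuous titer comparisons name no baseline adjustment, although the analysis set guarantees a pre-vaccination specimen. Within Cohort C, chance gaps above 0.5 SD are common (39% for 6 v 6, more against placebo), and rho times the gap passes into the unadjusted contrast. For 6 v 6, adjustment in one five-arm model shortens the interval by about 6%, 14% and 29% at rho 0.3, 0.5 and 0.7, of which 4 to 5 points are due to pooling.

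These figures rest on assumed correlations, a common slope, and equal, normal variances on the log scale. They apply to randomized contrasts within Cohort C, and by extension within Cohort D. Cohorts A, B and C were enrolled in sequence and are not randomized against each other, so a baseline difference between them need not be chance. Low severity: no stated decision is shown to turn on it.

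**What to change.** Add to Section 10.2: for each antigen and post-vaccination day, fit one linear model of log titer on arm and log Day 1 titer, across the randomized arms of Cohort C and, separately, of Cohort D if it is conducted. Report the adjusted GMT ratio with its 95% CI, and give the unadjusted result alongside. State in advance whether the equal-dose arms are merged at Day 29.

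Keep vaccine versus placebo within Cohorts A and B unadjusted or descriptive. Label any contrast across cohorts as non-randomized. State the common-slope and common-variance assumption, and say that it cannot be checked in a placebo arm of 2.

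The cost is wording in the analysis plan; no further specimens or participants are needed. The statistical price is one degree of freedom plus the imbalance term: about 3% wider for 12 v 8 if baseline turns out to be uninformative.
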